Study recruitment and retention	Research Meeting Report - RA to study team	Monitored frequently by PI at research team meetings
Enrollment and Randomization	Research meeting report of enrollment updates (inclusion and exclusion criteria) and tracking of assignment to condition	Monitored frequently by PI at research team meetings
Self-report data	RA will review data at participants' visits for completeness, accurate downloading of data, and tracking	Monitored frequently by PI at research team meetings
Intervention	A random selection of 20% of sessions for each therapist will be reviewed for therapist adherence to protocol by PI	Monitored at frequent clinical supervision

Confidentiality.

Confidentiality is assured as participants will be identified on all study materials only by participant number, visit number, and date of visit. By recording the study data in this manner, the information can be considered 'de-identified.'

F. Data safety and monitoring plan.

Regulatory Issues

The following procedures will be followed, in compliance with NIH requirements, to ensure the safety of study participants and the validity and integrity of data.

Mechanisms for reporting adverse events.

Adverse events are defined as harmful occurrences to study participants, either study related or non-study related.

At yearly intervals during the course of the study and then again at its completion, unblinded summaries of the numbers and rates of adverse events by treatment group will be summarized by the research team. These reports will include types of events, severity, and treatment phase. Data on individual non-serious adverse events is not expected to be needed.

Reporting of SAEs to the IRB and NIDA.

Expedited review will occur for all events meeting the FDA definition of Serious Adverse Events (SAEs; i.e., any fatal event, immediately life-threatening event, permanently or substantially disabling event, event requiring or prolonging inpatient hospitalization, or any

congenital anomaly). This also includes any event that a study investigator or the DSM Committee judges to impose a significant hazard, contraindication, side effect, or precaution. Additional reporting to site-specific IRBs will be done within 24 hours of the study team being made aware of the SAE. Reporting of any study-related SAEs and SAEs that severely impact participants (i.e., participant deaths) will be made to NIDA within 24-72 hours of the study team being made aware of the SAE.

Reporting of IRB actions to NIDA.

The principal investigator will report, via email, and, if appropriate hard copies of action logs or reports, of any major IRB actions. These will also be reported on the written, yearly progress report to NIDA. Minor amendments (i.e. advertisements, minor changes to procedures) are not regularly reported to NIDA.

Report of changes or amendments to the protocol.

Any changes to the protocol or amendments will be submitted to the IRB before they are implemented. For each yearly annual review, the detailed protocol will be updated and sent to the IRB as well.

Following guidelines by NIH, the NIDA project officer will be kept informed of any major changes to the protocol prior to being conducted via email from the principal investigator to the project officer. This will include any changes involving key personnel. Additionally, these changes will be recorded in the annual progress report submitted to the NIDA project officer.

Trial stopping rules.

There are no articulated stopping rules in advance of this study (i.e. for futility or for a stronger than expected effect). However, if at any time during the course of the study the Committee judges that risk to subjects outweighs the potential benefits, the Committee shall have the discretion and responsibility to recommend that the study be terminated. In such cases, the PI will immediately consult the DSM committee and consider the most appropriate course of action up to and including the immediate discontinuation of the intervention. There is no pre-specified stopping rule given the low anticipated risk of participation and small sample size. The power analysis is such that the full N would be required to make this determination. However, as with any DSMB, this DSMB will have the power to request analyses, post-randomization data, or any other information about the study, and has the power to suspend the study should they deem it necessary and a potential participant safety issue.

Disclosure of any conflict of interest.

Each investigator has completed a conflict of interest statement, which is kept on file by the study team and has been submitted to their respective institutions' IRBs. Any new investigators or key study staff will complete these forms, which will be stored kept on record. Any changes to conflict of interest statements will be reported to NIDA. Conflicts of interest will be disclosed to the DSMB at the time of each report. There are no financial conflicts of interests in this behavioral study, and no other conflicts of interests at this time.

Collection and reporting of AEs to SAEs

All staff will receive extensive training on ascertaining, monitoring, and documenting adverse events. The K23 mentors have extensive experience in clinical trials organization and management, including data safety monitoring for single site and multi-site trials. All investigators and study staff will be trained in monitoring and documenting adverse events. Expedited review will occur for all events meeting the FDA definition of Serious Adverse Events (SAEs). This also includes any event that a study investigator judges to impose a significant hazard or precaution. The study sites will report AEs and SAEs to the UCT site PI, [name],

and PI [name].

AEs will be labelled according to severity, which is based on their impact on the patient. An AE will be termed “mild” if it does not have a major impact on the patient, “moderate” if it causes the patient some minor inconvenience, and “severe” if it causes a substantial disruption to the patient’s well-being. A severe AE and an SAE are distinct terms. A subject could experience a severe AE that does not meet the above-listed definition of an SAE; alternatively, a subject could experience a moderate AE that meets the SAE definition. AEs will be categorized according to the likelihood that they are related to the study intervention. Specifically, they will be labelled definitely unrelated, definitely related, probably related, or possibly related to the study intervention.

For the purposes of this study, all SAEs will be required to be reported to the Committee, regardless of any judgment of their relatedness to the study. All relevant information will be reported to the DSMB for each SAE including information about the event and its outcome, study condition, concomitant medications, the subject’s medical history and current conditions, and all relevant laboratory data. This will be provided annually at the DSMB committee meeting.

Reporting to site-specific IRBs will be done within 24 hours of the study team being made aware of the SAE. Reporting of any study-related SAEs and SAEs that severely impact participants (i.e., participant deaths) will be made to NIDA within 24-72 hours of the study team being made aware of the SAE.

Non-Serious Adverse Events. At yearly intervals during the course of the study and then again at its completion, the DSMB will be provided with unblinded summaries of the numbers and rates of adverse events by treatment group. These reports will include types of events, severity, and treatment phase. Data on individual non-serious adverse events is not expected to be needed for this review.

Other Safety-Related Reports. At yearly intervals throughout the course of the study, the DSMB will also receive unblinded summary reports of treatment retention and reasons for dropout, by treatment arm and study phase.

Trial Efficacy

Plans for interim analysis for efficacy data.

If at any time during the course of the study, the Committee judges that risk to subjects outweighs the potential benefits or a safety concern arises, the Committee shall have the discretion and responsibility to recommend that the study be terminated. However, there are no pre-specified interim analysis for efficacy data given that (1) this is not an efficacy trial, rather a hybrid effectiveness-implementation trial; (2) the low anticipated risk of participation in the behavioral intervention and (3) small sample size. The power analysis is such that the full N would be required to make this determination. However, the DSMB will have the power to request analyses should they deem it necessary.

DSM Plan Administration

Responsibility for data safety and monitoring.

The principal investigator and primary mentor are ultimately responsible for data and safety monitoring. The processes described above ensure that the principal investigator will be aware of important study related issues on a regular basis. If any staff becomes aware that an adverse event occurs, this will immediately report it to the principal investigator and site project director. In addition, a yearly DSM committee review of all SAEs will occur.

To fulfil its mission of ensuring the safety and integrity of the study, it is necessary that the DSM Committee be comprised of members who possess a high degree of competence and experience, as well as the ability to function independently of all other parties involved in the

study. The DSMB members will function free of the career and financial interests of its members and will consist of three members with experience in conducting clinical intervention research for psychiatric and substance use disorders, expertise in biostatistics, and a thorough knowledge of clinical trial ethics and human subject protection issues.

Frequency.

The DSM Committee will be updated annually with a report containing randomization data as well as adverse events. These adverse events are tracked for IRB submission as well. All SAEs are reported annually at continuing review. The DSM Committee will be comprised of nominees from both the Cape Town and US study sites.

Content of DSM report

The DSM report will include a tally and description of adverse events and serious adverse events. It will include a description of how these were handled, which experimental group the participant was assigned to (treatment or control), and if and how the participants' physician was notified. The DSM meeting will also involve a presentation from the P.I. regarding any emerging clinical issues involved in delivering the treatment, expected versus actual recruitment rates, treatment retention rates, any quality assurance or regulatory issues that occurred during the past year relevant to the trial, and any actions or changes with respect to the protocol. Sections of the DSM report will include:

- A. Brief description of the trial
- B. Baseline sociodemographic characteristics
- C. Retention and disposition of study participants
- D. Q.A. Issues
- E. Regulatory Issues
- F. AEs
- G. SAEs
- H. Efficacy

DSM Board Plan

Members. The Data and Safety Monitoring Board (DSMB) will function as an independent body charged with ensuring that the safety of study subjects is protected in Phase 3 and that the scientific goals of the study are being met. To support those purposes, the DSMB will review any proposed major amendments to the study protocol at the annual review, perform ongoing monitoring of drop-outs and all adverse events, determine whether study procedures should be changed or the study should be halted for reasons related to the safety of study subjects, and perform periodic review of the completeness and validity of data to be used for analysis of safety and efficacy. The DSMB will also ensure subject privacy and research data confidentiality. The DSM Committee will include both US- and South Africa-based investigators.

The Chairperson of the DSMB will communicate by e-mail and telephone conference with the other members. Reporting and communication about other matters will occur on a yearly basis, for the duration of Phase 3. Decisions of the DSMB will be made based on a majority vote of the members.

Conflict of interest. The DSMB members will function free of the career and financial interests of its members.

Protection of confidentiality. Adverse event reports and annual summaries will not include identifiable information. Each report will only include the participants' identification numbers.

Monitoring activities. At a minimum, the DSMB report includes an overview of the progress of participant intake and retention; summary reports describing participant compliance with visits, evaluations, and dosing as described in the protocol; a summary of all adverse events and major amendments to the protocol; and a summary of the completeness and quality

of key data elements needed to characterize participants, their dosing, and their primary and secondary outcomes. These reports are used by the DSM Committee to evaluate the capacity of the data capture and processing to support scientifically valid analyses. For ease of understanding, reports are done graphically, similarly to the CONSORT figures.

Communication plan to IRB and NIDA. The annual IRB Continuing Review will include the DSMB report for review. DSMB activity will be reported in annual NIH progress reports when applicable.

LIST OF MEASURES

A description of each measure can be found above in the outcomes section.

Table 1. Measures at Major Assessments

Measure	Screening	Baseline	Post-Treatment	6- Month Follow-Up
Demographics		X		
Mode of HIV Infection		X		
AUDIT		X	X	X
WHO-ASSIST	X		X	X
Substance Use History Questionnaire		X	X	X
Economics & RUQ		X	X	X
Sexual Risk-Taking Questions		X	X	X
ACTG- SF-21		X	X	X
Barriers to Adherence		X	X	X
Robbed, Recreational ARVs		X	X	X
Brief RCope		X	X	X
PHQ-9		X	X	X
PTQ		X	X	X
BADS		X	X	X
RPI		X	X	X
SOCRATES		X	X	X
SIP		X	X	X

PACS		X	X	X
Interactive Toxicity Beliefs Questionnaire		X	X	X
Ira Wilson's Three-Item Self-Report Measure		X	X	X
Substance Use and HIV Related Stigma Scale (SU and HIV- SMS)		X	X	X
Acceptability/Feasibility Questionnaire			X	X
Urinalysis		X	X	X
Blood Draw (DBS; CD4 count and viral load – when results not available in clinic records in past 3 months for baseline/ 30 days for follow-ups)		X	X	X
Chart Extraction		X	X	X
Wisepill		X	X	
Timeline Follow-Back		X	X	X
Exit Interview (subset of intervention participants)				X

Table 2. List of Measures During Intervention
(Participants randomized to intervention condition only)

Measure	S1	S2	S3	S4	S5	S6
SRA Weekly Adherence	X	X	X	X	X	X
Wisepill	X	X	X	X	X	X
Timeline Followback*	X*	X	X*	X	X	X
Urinalysis*			X*			

*Control participants will also be invited to the clinic for urinalysis and timeline follow-back approximately 5-weeks post-randomization (approximately equivalent in time to Session 3). Control participants will also do timeline follow-back at their randomization visit (corresponding to intervention participants' Session 1).

REFERENCES

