Additionally, individuals who have failed first-line ART are at risk for ongoing nonadherence because they did not achieve viral suppression with first line agents. By selecting these multiply challenged patients from the clinics, the potential impact of the intervention is maximized in that, if successful, it will minimize the chances that these patients will need third-line treatment, not currently available in public SA clinics. The long-term success of TasP relies on addressing substance use and ART adherence.

Finally, the use of real-time wireless electronic adherence monitoring technology is an innovative strategy for real-time assessment of our primary outcome, ART adherence. This study will provide important pilot data on the acceptability and feasibility of real-time wireless monitoring among HIV-infected substance users in sub-Saharan Africa.

C. PRELIMINARY STUDIES

Paraprofessional counsellors can reliably screen for substance use in Cape Town. [name] recently collaborated with co-mentors Drs. [name] and [name] to document the feasibility of lay counselor screening for substance use using the WHO-ASSIST, the proposed screening tool in this study for patients presenting to a co-located substance use/HIV treatment setting.^{35,36} Additionally, in other studies, co-mentor [name] has shown that lay counselors can reliably screen for and detect substance use in HIV care in South Africa with good sensitivity (94%) and specificity (85%).^{26,27}

Paraprofessional counsellors can be trained in and deliver problem solving and behavioral activation-based interventions in sub-Saharan Africa. [name], K co-mentor, has led a series of studies in South Africa showing the feasibility of training peer counselors to deliver problem solving, MI, and behavioral activation. Additionally, these studies have shown significant reductions in substance use at a three month follow up.^{18,19,21} [name] and [name] co-trained five lay counselors in Zimbabwe in a problem solving intervention for adherence, which was found to be feasible and acceptable.^{37,38} Other work led by Drs. [name], [name], and [name] has demonstrated the feasibility and acceptability of a nurse-delivered problem solving intervention for adherence, which was associated with increases in ART adherence over 3 months ($p=.01$), and >90% retention.³⁹

There is evidence that problem solving for ART adherence may need tailoring for

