clinic as failing first line treatment in the past 3 months: VL > 400 copies/mL, on second-line treatment, reinitiated on first-line treatment within the past three months, or pharmacy non-refill at least once in the past three months) will be screened for substance use. Eligible patients will be briefed on study procedures, and if interested, will provide informed consent. All individuals meeting inclusion criteria will be provided the opportunity to participate.

Based upon preliminary studies and published work screening for substance use in HIV care^{7,26,27} the study estimates to recruit 1-2 eligible patients per week. At this rate, the study can conservatively estimate recruiting and randomizing 60 patients feasibly within 1.5 years.

Retention. Bilingual research assistants will track retention. Staff will be trained to place reminder calls to participants 1 week and then three days prior to each scheduled follow-up session. This approach has been used successfully in past work by the US team, and has achieved an 84% retention rate at 3-month follow-up. Each participant will also be asked for updated contact information (e.g. phone number, address) at each follow-up assessment to ascertain if phone numbers have changed.

C. Study Procedures

Study setting. This study will be conducted through the University of Cape Town (UCT). The proposed clinic (where Phase 1 data collection also occurred) and where the parent study (010/2014) is being conducted is the Town II clinic in Khayelitsha.

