Study procedures. Study procedures are illustrated in Figure 2 (below). Participants who meet screening criteria and would like to be part of the study will go through an informed consent process, described above. Following consent procedures, participants will complete the baseline assessment. When the baseline assessment is finished, all eligible participants will receive a wireless adherence monitoring device, also known as Wisepill. Participants will then use the device for two weeks to enable two weeks of wireless medication monitoring as a baseline assessment of ART adherence. Approximately two weeks after the baseline

assessment, participants will be invited to come back to the clinic for randomization. Participants will be randomized into either 1) the intervention group (the paraprofessional adapted intervention to improve ART adherence and substance use) or 2) the control group (the enhanced standard of care). Randomization assignment will not affect patients' use of other ART clinic services. Regardless of condition, participants who attend all mandatory visits (intervention: all assessments and all six intervention sessions; control: all assessments and midpoint urinalysis) will receive a completion certificate at the end of their final assessment (six-month follow-up assessment).

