4. Chart Extraction: Patients who provide informed consent will also be invited to sign a release of information to allow access to their medical record for current ART regimen, time on ART, viral load, CD4 count, tuberculosis (TB) treatment information, mental health information (including diagnoses and substance use treatment referrals) and appointment attendance (HIV treatment program and Matrix if applicable). This information will be specifically extracted from their medical charts at all major assessments.

E. Data analytic plan.

Power calculation and sample size.

The study plans to enroll 60 participants. The main analysis which the sample size calculation was based on is the effect of the intervention vs. enhanced standard of care on ART nonadherence (Wisepill) at 6 months. Previous objective measures of ART adherence in substance using populations have estimated average adherence of approximately 55% with a standard deviation of 0.25.⁷⁴⁻⁷⁶ Assuming similar characteristics in standard of care, and based on a sample size of 30 in each arm as recommended as the upper limit sample size for pilot RCTs, the study will have 80% power to detect an 18% difference in objectively measured ART adherence between study arms using a two-sided test with an alpha level of 0.05. Given that the intervention will be adapted and has not been implemented prior in this setting, the table has been included below to demonstrate the levels of power based on varying differences in average adherence that may be detected between groups. These estimates are based on 30

participants in each arm, in keeping with the recommendations for pilot RCTs and pilot,⁷⁷ Type I hybrid-effectiveness-implementation designs.^{23,53}

Data analytic plan.

Quantitative longitudinal analysis will examine changes in primary effectiveness outcomes: 1) ART nonadherence; 2) substance use; 3) and viral load (exploratory) from baseline to 6-month follow-up between the conditions. Descriptive measures will be used to summarize data (e.g., means, SD, median, IQR for continuous variables). Exact binomial confidence intervals will be used to estimate confidence intervals for categorical variables.

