Statistical tests (such as t-test and Wilcoxon rank sum test) will be used to compare continuous study outcomes (e.g., ART nonadherence) between the two arms at baseline. For comparison of categorical outcomes (e.g., urinalysis), Fisher's exact test will be used. Longitudinal data analysis using generalized linear mixed models (GLMM) will be used to compare the study endpoints (ART nonadherence, substance use, viral load at 6 months) between the two arms after adjusting for the effect of other covariates (e.g., gender, age). This approach increases power by including all available data points. Intent-to-treat will be utilized, where all individuals will be analyzed according to the condition that they were randomized. Effect size estimates will be generated to provide estimates to power for a larger future grant application.

Table 1. Levels of power based on varying differences in adherence detected.

Predicted Avg Adherence in Control Group	Predicted Avg Adherence in Tx Group	Difference in Avg Adherence	SD of Estimated Adherence	Power
0.55	0.85	0.30	0.25	0.99
0.55	0.80	0.25	0.25	0.97
0.55	0.75	0.20	0.25	0.88
0.55	0.73	0.18	0.25	0.80
0.55	0.70	0.15	0.25	0.64
0.55	0.65	0.10	0.25	0.34

ETHICAL CONSIDERATIONS AND RISKS TO THE SUBJECTS

A. Risks to participants.

Human subjects involvement and characteristics.

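### The 80% power for an 18-point adherence difference assumes no missing Wisepill data; unadjusted, it falls to about 78%, 75% or 72% at assumed losses of 5%, 10% or 16%

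*Protocol*

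**What the plan says.** In the protocol's Data analytic plan, under Power calculation and sample size, planned enrolment is 60. The calculation is "based on a sample size of 30 in each arm" and concludes that "the study will have 80% power to detect an 18% difference in objectively measured ART adherence between study arms". The inputs are control adherence of about 55%, an SD of 0.25 and a two-sided alpha of 0.05. The accompanying table, titled "Levels of power based on varying differences in adherence detected", gives power for differences from 10 to 30 points, all on 30 per arm. The outcome being powered is "the effect of the intervention vs. enhanced standard of care on ART nonadherence (Wisepill) at 6 months".

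Neither document gives a dropout allowance, an inflation of the sample size or an expected rate of missing Wisepill data. Two retention figures appear elsewhere, both from other work. Under Retention, the approach planned here "has achieved an 84% retention rate at 3-month follow-up" in the US team's past work. Under Preliminary Studies, a nurse-delivered adherence intervention is reported with a gain in adherence "and >90% retention".

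The planned analysis is a generalized linear mixed model. Participants use the device for two weeks before randomization "to enable two weeks of wireless medication monitoring as a baseline assessment of ART adherence".

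**The concern.** Enrolled and analysed numbers are the same, so the power figure has no room for loss. The protocol nevertheless expects data problems. The Wisepill outcome description plans adjustments for device malfunction and lost signal, and the battery-monitoring section adds a mid-point check-in and charging to protect the data. Participants are also selected because they struggle with adherence and use substances.

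The figure is relied on in two places. The sections on stopping rules and interim efficacy analysis both cite the power analysis as needing the full sample. The Data analytic plan adds that "Effect size estimates will be generated to provide estimates to power for a larger future grant application", so readers need to know what this trial could detect.

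The time point is a second problem in the same section. If no Wisepill data are collected at 6 months, the power statement describes an analysis that cannot be done.

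**Working it through.** **Inputs from the protocol.** Difference d = 0.18 (0.55 against 0.73), SD = 0.25, two-sided alpha = 0.05 (z = 1.96), n = 30 per arm.

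**Inputs assumed.** Loss of 5% has no source in the documents. Loss of 10% is the upper bound implied by retention above 90%. Loss of 16% is 100% − 84%. The last two are retention in other studies, not rates of missing Wisepill data. Loss is taken as equal in both arms, with the SD unchanged.

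**Formula (normal approximation).** SE = SD × √(2/n); power ≈ Φ(d/SE − 1.96).

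**Reproducing the stated figure.** SE = 0.25 × √(2/30) = 0.0645. Then 0.18/0.0645 = 2.789, 2.789 − 1.96 = 0.829, and Φ(0.829) = 0.796. The whole table at 30 per arm:

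| Difference (points) | 30 | 25 | 20 | 18 | 15 | 10 |
|---|---|---|---|---|---|---|
| Printed | 0.99 | 0.97 | 0.88 | 0.80 | 0.64 | 0.34 |
| Recomputed | 0.996 | 0.972 | 0.873 | 0.796 | 0.642 | 0.341 |

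Every entry agrees to within 0.01. The printed values therefore correspond to an unadjusted comparison with all 60 evaluable. There is no slack: the same formula needs 31 per arm to reach 80% at 18 points.

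**Adding loss, 18-point difference.** The last row uses 25 per arm, the whole number below 30 × 0.84 = 25.2; at exactly 25.2 the normal figure is 0.724.

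| Loss | n per arm | Power, normal | Power, t-test | 80%-power difference, normal | 80%-power difference, t-test |
|---|---|---|---|---|---|
| none | 30 | 0.796 | 0.783 | 18.1 | 18.4 |
| 5% | 28.5 (57 in total) | 0.776 | 0.761 | 18.6 | 18.9 |
| 10% | 27 | 0.753 | 0.738 | 19.1 | 19.4 |
| 16% | 25 | 0.721 | 0.703 | 19.8 | 20.2 |

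Detectable differences are in percentage points. Compared within one method, the cost in power is about 2, 4 and 7 to 8 points.

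**What baseline adjustment would have to supply.** With a baseline-outcome correlation r, the variance is multiplied by (1 − r²). To regain 80%, √(1 − r²) must equal (d/SE)/(1.96 + 0.842). At 27 per arm, d/SE = 2.645, so √(1 − r²) = 2.645/2.802 = 0.944 and r = 0.33. The values needed at 5%, 10% and 16% loss are 0.24, 0.33 and 0.42 (normal), or 0.30, 0.38 and 0.46 (t-test).

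**Time point, side by side.**
- Power section: Wisepill at 6 months.
- Assessment visits: the device is handed back at the post-treatment assessment, about 3 months after baseline.
- Wisepill outcome description: the only time frame is about 10 weeks after randomization.
- Table of measures at major assessments: the Wisepill row has entries at baseline and post-treatment and none at 6 months.
- SAP, Effectiveness Outcomes: change from baseline to post-treatment.

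**The case against.** The strongest reply is that the stated 80% is correct on its stated n, and that power did not set the sample size. Thirty per arm comes from a recommended upper limit for pilot trials, and the table already shows power from 0.34 to 0.99. Moving from an 18-point to a 15-point effect alone takes 0.80 to 0.64, more than any loss considered here. This stands: the point concerns an omitted allowance, not a miscalculation, and the shortfall is modest.

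Second, the loss rates are not the trial's own. Wisepill transmits without a clinic visit, so a missed visit need not mean a missing outcome, and a partial record can still give a percentage of doses. That also stands, and is why the result is a range. Remote transmission does not cover device failure or non-use, so the true rate could be lower or higher.

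Third, the planned analysis is a longitudinal model with a baseline on the same device, and moderate correlations would restore 80%. This is possible but cannot be credited from the documents. They give no correlation, name gender and age as example covariates, and put no gain into the power figure. The SAP makes the mixed model conditional on its assumptions being met and allows t-tests.

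Fourth, planning a larger study depends on precision more than on power at 18 points. At 16% loss the standard error rises by about 9% (√(30/25.2) = 1.09), and the unadjusted 95% half-width goes from about 12.7 to 13.8 points. That is fair, but it is also a consequence of loss that the plan does not mention.

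**Conclusion.** The concern holds. The power statement assumes complete follow-up adherence data on all 60 participants, and nothing in either document supports or adjusts for that. For the unadjusted comparison, the chance of missing a true 18-point difference rises from about 20% to 22%, 25% and 28% at 5%, 10% and 16% loss. These figures rest on the assumed loss rates, equal loss in the arms and no gain from baseline adjustment. Whether the planned model closes the gap cannot be judged without a correlation.

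The 6-month inconsistency needs no assumption. It does not alter the arithmetic, but it means that the power section must be edited in any case.

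**What to change.** Keep the sample size at 60. In the power section:

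1. State the assumed proportion of participants without usable follow-up Wisepill data.
2. Restate the power by one named method. Suggested wording: With 27 to 25 evaluable per arm (10% to 16% loss), power for an 18-point difference is about 75% to 72%, and the difference detectable with 80% power is about 19 to 20 points (unadjusted, normal approximation).
3. Recompute the table by the same method:

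| n per arm | 30 points | 25 | 20 | 18 | 15 | 10 |
|---|---|---|---|---|---|---|
| 30 | 1.00 | 0.97 | 0.87 | 0.80 | 0.64 | 0.34 |
| 27 | 0.99 | 0.96 | 0.84 | 0.75 | 0.60 | 0.31 |
| 25 | 0.99 | 0.94 | 0.81 | 0.72 | 0.56 | 0.29 |

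   At 30 per arm this changes two printed entries, by rounding only: 0.88 to 0.87 at 20 points, and 0.99 to 1.00 (0.996) at 30 points.
4. If baseline adjustment is relied on to recover power, say so, and state and justify the assumed correlation.
5. Reconcile the 6-month Wisepill outcome with the device's return at about 3 months and the SAP's post-treatment analysis, so that the power refers to a time point at which adherence is measured.

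The cost is a change of text and one table, with no change to recruitment or procedures. The stated power becomes less favourable unless a correlation is justified.
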